5.4 Withdrawal of Subjects

5.4.1 Withdrawal of Subjects from Study Drug

Study drug must be stopped if the subject experiences any kind of hypersensitivity reaction related to the study drug during administration. The subject concerned will remain under follow-up and the subsequent visits should be performed in accordance with the protocol schedule. Whether the subject should receive additional doses of study treatment will be discussed with the Medical Monitor and will be decided on a case by case basis. If study drug is stopped prematurely for any one subject, the subject concerned will not be replaced.

Subjects may be withdrawn from the study drug if in the opinion of the Medical Monitor or the Investigator there would be a risk to the subject's safety if they received any further dose of study drug.

Following section in italics is applicable for The Netherlands, Spain and Singapore only (**NL, ES and SG only**):

Subjects enrolled in the study with Hb levels that are falling below the threshold of 10 g/dL during the study will need to be withdrawn from further study treatment dosing.

If study treatment is stopped prematurely for a subject, follow-up for the subject concerned should continue in accordance with the protocol schedule. The discontinuation of study treatment is mandatory in circumstances that therapies or treatments listed in Section 7.7.2 as restricted need to be applied to the subjects for general health reasons. Discontinuation of study treatment is also mandatory in the case a subject enrolled into the study is getting pregnant (see Section 10.3.3 for reporting instructions).

The reason for study-drug discontinuation and the date must be recorded on the appropriate page of the eCRF. The follow-up of these subjects should continue in accordance with the protocol schedule.

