10.3.3 Pregnancy

When a female subject becomes pregnant during the study and study treatment has been administered to the subject, the outcome of the pregnancy needs to be monitored and the safety of the mother and unborn child need to be safeguarded (as per protocol, pregnancy is an exclusion criteria). Therefore, the outcome of all such pregnancies (including normal births) must be followed up and documented, even if the subject was withdrawn from the study or the study has been completed.

Women of childbearing potential should have a negative serum pregnancy test prior to randomisation. Study treatment should not be initiated by the Investigator until a report of a negative pregnancy test has been obtained.

A highly effective contraception must be used in female subjects of childbearing potential before beginning study treatment, during study dosing, and for 30 days following discontinuation of study treatment.

Following sections in italics are applicable for United Kingdom only (**UK only**):

Highly effective birth control methods include:

- *Combined (oestrogen and progestogen containing) hormonal contraception associated with inhibition of ovulation*

- *Oral*
- *Intravaginal*
- *Transdermal*
- *Progestogen-only hormonal contraception associated with inhibition of ovulation*
 - *Oral*
 - *Injectable*
 - *Implantable*
- *Intrauterine device*
- *Intrauterine hormone-releasing system*
- *Bilateral tubal occlusion*
- *Vasectomised partner*
- *Sexual abstinence*

Due to the follow-up of 52 weeks per patient after randomisation in the present study, sexual abstinence is only acceptable as 'true abstinence' when this is in line with the preferred and usual lifestyle of the subject. Periodic abstinence (e.g., calendar, ovulation, symptothermal, post-ovulation methods), declaration of abstinence for the duration of exposure to IMP, and withdrawal are not acceptable methods of contraception.

A female subject must immediately inform the Investigator if she becomes pregnant during the study and no further study treatment shall be administered. The Medical Monitor must be contacted immediately to break the blind (if applicable). The Investigator should counsel the subject and discuss the risks of continuing with the pregnancy and the possible effects on the foetus.

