4.8.1. Treatment Exposure and Compliance

Time on study (follow-up) in weeks and subject-years on study as defined in sections 4.2.14 and 4.2.18 will be summarised as continuous variables. Time on study drug as defined in section 4.2.15 will also be summarised.

Treatment Exposure

The number of injections of study drug per subject will be summarised as a categorical variable (1, 2, 3, 4). The total amount of study drug given and planned (see Table 6 and Table 7) across

visits (mL) will be calculated for each subject, and will be summarised by treatment group. Summary statistics for the doses received (in mL and in mg) at each visit be also presented.

The total amount of study drug and the doses received at each visit in mL and mg will also be summarised as a continuous variable.

Treatment Compliance

The planned dose will be derived based on the protocol number, protocol consent and re-consent dates, serum pregnancy test result, weight, Hb levels, and ID status as per Table 6 and Table 7 below. Table 7 will apply only for subjects who consented to protocol 2 or 3 or if the subject re-consented to protocol 2 and the injection date is on or after the protocol re-consent date. ID is defined as serum ferritin <100 ng/mL, or $100 \text{ ng/mL} \leq \text{serum ferritin} \leq 299 \text{ ng/mL}$ if transferrin saturation (TSAT) is <20%. The laboratory and vital sign values closest to the injection date and time (\leq) will be used. In case no injection was done, the value closest to the visit date will be used.

For the protocol 1, the first dose of study treatment is administered for all randomised subjects on the same day as randomisation – i.e., at Visit 2 while the subject is still hospitalised for the Index hospitalisation. The subsequent administrations of study treatment are done as part of the outpatient clinic visits at Week 6 (Visit 3), and at Weeks 12 (Visit 4) and 24 (Visit 5) only for subjects in whom ID persists and for whom $\text{Hb} \geq 8 \text{ g/dL}$ and $\leq 15 \text{ g/dL}$. The serum pregnancy test must also be negative for the respective visit for females of childbearing potential.

The dosing regimen for protocol 1.2 is similar to the one from protocol 1 except for the subjects from The Netherlands (NL). For NL subjects, the lower threshold of Hb values is set to 10 g/dL.

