For the protocol 2 and 3, dosing at Week 6 (Visit 3) is based on the iron need upon screening Hb and weight values to replete iron as described in Table 7 and only be done in subjects for whom $\text{Hb} \leq 15 \text{ g/dL}$. Maintenance dosing at Weeks 12 (Visit 4) and 24 (Visit 5) is only for subjects in whom ID persists and for whom $\text{Hb} \geq 8 \text{ g/dL}^*$ and $\leq 15 \text{ g/dL}$ at those visits. The serum pregnancy test must also be negative for the respective visit for females of childbearing potential.

* Following section in italics is applicable for The Netherlands, Spain and Singapore only (**NL, ES and SG only**):

The lower threshold of Hb values is set to 10 g/dL.

Table 6 Study drug Dosing Regimen Protocol 1

Treatment Visit	Total mL FCM or Saline				
	Weight <70 kg		Weight ≥70 kg		Any Weight
	8 g/dL ≤ Hb < 10 g/dL	10 g/dL ≤ Hb ≤ 14 g/dL	8 g/dL ≤ Hb < 10 g/dL	10 g/dL ≤ Hb ≤ 14 g/dL	
Visit 2 (Week 0)	2x10 mL				1x10 mL
Visit 3 (Week 6)	1x10 mL (only if ID persists)	No dose	2x10 mL (only if ID persists)	1x10 mL (only if ID persists)	No dose
Visit 4, Visit 5 (Week 12, Week 24)	1x10 mL (only if ID persists)				

Notes: FCM=Ferric carboxymaltose; Hb=Haemoglobin; ID=Iron deficiency.

Table 7 Study drug Dosing Regimen Protocols 2, 3

Treatment Visit	Total mL FCM or Saline				
	Weight <70 kg		Weight ≥70 kg		Any Weight
	8 g/dL ⁽¹⁾ ≤ Hb <10 g/dL	10 g/dL ≤ Hb ≤14 g/dL	8 g/dL ⁽¹⁾ ≤ Hb <10 g/dL	10 g/dL ≤ Hb ≤14 g/dL	
Visit 2 (Week 0)	2x10 mL				1x10 mL
Visit 3 ⁽²⁾ (Week 6)	1x10 mL	No dose	2x10 mL	1x10 mL	No dose
Visit 4, Visit 5 (Week 12, Week 24)	1x10 mL (only if ID persists)				

1 Following section in italics is applicable for The Netherlands, Spain and Singapore only (NL, ES and SG only): *The lower threshold of Hb values for subject eligibility prior to enrolment into the study is set to 10 g/dL. Subjects enrolled in the study in NL, ES and SG only with Hb levels that are falling below the threshold of 10 g/dL during the study will need to be withdrawn from further study treatment dosing.*

2 Dosing at Week 6 (Visit 3) will be based on the iron need upon screening Hb and weight values and only be done in subjects for whom Hb at Week 6 (Visit 3) ≤15 g/dL.

Notes: FCM=Ferric carboxymaltose; Hb=Haemoglobin; ID=Iron deficiency.

The algorithm to calculate the planned dose is described in Appendix II.

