The calculated planned dose and the dose administered as collected in the eCRF will be used to calculate the dosing information (dose given as planned, reduced, increased). It will be summarised for each treatment visit (Baseline, Visit 3 [Week 6], Visit 4 [Week 12], and Visit 5 [Week 24]).

The total amount of study drug given during the study will be calculated for each subject and will be compared to the amount expected to be given for each subject based on weight, Hb levels, and ID status. Treatment compliance will be calculated for each subject and summarised by treatment group and summarised as continuous and categorical variable (<80, 80-120, > 120 as categories)

- Total amount = total volume administered in mL over all visits.
- Expected amount = total volume in mL that should have been administered as described in Table 6.
- Compliance rate = (total amount/expected amount)*100.

Treatment compliance and drug concentration information will also be reported in data listings.

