Appendix II: Calculation of planned dose

Protocol Number	Planned Dose
1, 1.1, 1.2 and country NE The Netherlands, Singapore, Spain	
"Hemoglobin in g/dL" < 8: No dose "Hemoglobin in g/dL" > 15: No dose
 
Visit 2 If "Serum pregnancy test" = "Positive": No dose 8 ≤ "Hemoglobin in g/dL" ≤ 14: 2 Kits 14 < "Hemoglobin in g/dL" ≤ 15: 1 Kit
 
Visit 3 If "Serum pregnancy test" = "Positive": No dose "Weight in kg" < 70 and 8 ≤ "Hemoglobin in g/dL" < 10 and "ID persists" : 1 Kit "Weight in kg" < 70 and 10 ≤ "Hemoglobin in g/dL" ≤ 14 : No dose "Weight in kg" ≥ 70 and 8 ≤ "Hemoglobin in g/dL" < 10 and "ID persists" : 2 Kits "Weight in kg" ≥ 70 and 10 ≤ "Hemoglobin in g/dL" ≤ 14 and "ID persists" : 1 Kit "Hemoglobin in g/dL" > 14 : No dose
 
Visit 4 and Visit 5 If "Serum pregnancy test" = "Positive": No dose "ID persists" : 1 Kit

2, 3 and country NE The Netherlands, Singapore, Spain	
"Hemoglobin in g/dL" < 8: No dose "Hemoglobin in g/dL" > 15: No dose
 
Visit 2 If "Serum pregnancy test" = "Positive": No dose 8 ≤ "Hemoglobin (from screening) in g/dL" ≤ 14: 2 Kits 14 < "Hemoglobin (from screening) in g/dL" ≤ 15: 1 Kit
 
Visit 3 If "Serum pregnancy test" = "Positive": No dose "Weight in kg" < 70 and 8 ≤ "Hemoglobin (from screening) in g/dL" < 10 : 1 Kit "Weight in kg" < 70 and 10 ≤ "Hemoglobin (from screening) in g/dL" ≤ 14 : No dose "Weight in kg" ≥ 70 and 8 ≤ "Hemoglobin (from screening) in g/dL" < 10: 2 Kits "Weight in kg" ≥ 70 and 10 ≤ "Hemoglobin (from screening) in g/dL" ≤ 14 : 1 Kit "Hemoglobin in g/dL" > 14 : No dose
 
Visit 4 and Visit 5 If "Serum pregnancy test" = "Positive": No dose "ID persists" : 1 Kit

Protocol Number	Planned Dose
If country = The Netherlands, Singapore, Spain	Same calculation as described above applies depending on protocol version. However, replace lower threshold for Hemoglobin by 10 g/dL instead of 8 g/dL.

Note:

ID is defined as serum ferritin <100 ng/mL, or $100 \text{ ng/mL} \leq \text{serum ferritin} \leq 299 \text{ ng/mL}$ if transferrin saturation (TSAT) is <20%. The laboratory and vital sign values closest to the injection date and time (\leq) is used. In case no injection was done, the value closest to the visit date will be used.

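### For the Netherlands, Spain and Singapore under protocols 2 and 3, SAP Appendix II plans doses again after a haemoglobin stop that SAP Table 7 and protocol 5.4.1 apply to all further dosing

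*SAP*

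**What the plan says.** SAP 4.8.1 (Treatment Compliance) says that the planned dose is "derived based on the protocol number, protocol consent and re-consent dates, serum pregnancy test result, weight, Hb levels, and ID status", and it points to the dosing tables: "ID status as per Table 6 and Table 7 below". Table 7 governs subjects who consented to protocol 2 or 3. It also governs injections on or after the date of re-consent to protocol 2.

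Table 7 footnote 1 has two parts for the Netherlands, Spain and Singapore. One raises the eligibility threshold to 10 g/dL. The other says that enrolled subjects whose Hb is "falling below the threshold of 10 g/dL during the study will need to be withdrawn from further study treatment dosing". Protocol Table 1 footnote 1 and protocol 5.4.1 carry the same stop.

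Appendix II turns the tables into an algorithm. Hb outside the permitted range means no dose at that visit. At Visits 4 and 5 one kit is planned if iron deficiency (ID) persists. For the three countries the only change is to "replace lower threshold for Hemoglobin by 10 g/dL instead of 8 g/dL". Laboratory values are those closest to the injection or, if none was given, closest to the visit.

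Compliance is the volume given divided by the volume expected, reported as a percentage and in the categories below 80, 80 to 120, and above 120. The denominator is defined as follows: "Expected amount = total volume in mL that should have been administered as described in Table 6". That line names Table 6 only. I read it together with the derivation sentence, so that Table 7 applies under protocols 2 and 3.

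**The concern.** The footnote is a lasting stop and the algorithm is a test at each visit. They agree at the visit where Hb is below 10 g/dL. They part at any later visit where Hb has recovered and ID persists: the footnote allows nothing, and Appendix II plans a kit. Follow-up visits and blood tests continue after a stop (protocol 5.4.1), so the algorithm will have the values it needs to plan that kit. A programmer cannot satisfy both instructions.

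What is at stake is the reading of the compliance tables. A site that obeyed the stop appears in the below-80 category and, if an omitted injection is entered as zero, as reduced in the by-visit table. The error also runs the other way: a subject wrongly re-dosed after recovery would look fully compliant.

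**Working it through.** The plan states no figure on this point, so there is none to reproduce. The check applies the SAP's compliance formula to subjects who obey every rule.

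**Inputs (SAP Table 7).** Three strata are possible with screening Hb of at least 10 g/dL. Volumes at Visit 2 / Visit 3:
- under 70 kg, Hb 10–14: 20 / 0 mL
- 70 kg or more, Hb 10–14: 20 / 10 mL
- Hb above 14 to 15, any weight: 10 / 0 mL

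Visits 4 and 5 (Weeks 12 and 24): 10 mL each if ID persists.

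**Assumptions.** Doses before the stop are given as planned and none is given afterwards. Hb is 10–15 g/dL at the visits after the fall, and no pregnancy test is positive. Recovery delayed until Week 24 gives the same volumes as ID at Week 24 only.

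**Formulas (Appendix II as written).** V2 and V3 are the Visit 2 and Visit 3 volumes; W12 and W24 are the Week 12 and Week 24 volumes.
- Hb below 10 at Week 6 (no Visit 3 dose): compliance = V2 / (V2 + W12 + W24)
- Hb below 10 first at Week 12 (no Week 12 dose): compliance = (V2 + V3) / (V2 + V3 + W24)

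| Hb first below 10 at | ID at later visits | <70 kg, Hb 10–14 | ≥70 kg, Hb 10–14 | Hb >14–15 |
|---|---|---|---|---|
| Week 6 | neither | 20/20 = 100% | 20/20 = 100% | 10/10 = 100% |
| Week 6 | Week 12 or Week 24 only (two patterns) | 20/30 = 66.7% | 20/30 = 66.7% | 10/20 = 50% |
| Week 6 | both | 20/40 = 50% | 20/40 = 50% | 10/30 = 33.3% |
| Week 12 | not at Week 24 | 20/20 = 100% | 30/30 = 100% | 10/10 = 100% |
| Week 12 | at Week 24 | 20/30 = 66.7% | 30/40 = 75% | 10/20 = 50% |

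**Count.** There are 3 strata × (4 + 2) ID patterns = 18 patterns. Six score 100% because no later dose would be planned anyway. The other 12 score 33.3% to 75%, all in the below-80 category.

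**With the stop carried forward**, expected equals given in every pattern and all 18 score 100%.

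**Reverse case.** Take screening Hb 10–14, a fall at Week 6, and doses wrongly given at Weeks 12 and 24. Appendix II gives 40/40 = 100%. The footnote gives 40/20 = 200%, in the above-120 category.

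**The case against.** The best defence is that Appendix II matches the running text of SAP 4.8.1. That text decides maintenance dosing on Hb at the visit itself, with a lower limit of 10 g/dL in the three countries. This is true, but it states a condition that must hold before a dose is given. It does not reinstate a subject who has been withdrawn. The footnote also keeps the threshold and the withdrawal as separate statements, so the withdrawal cannot be read as the threshold restated.

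A second defence is that compliance may properly measure delivered volume against the regimen, whatever the reason for stopping. SAP 4.8.1 bases the expected amount on weight, Hb levels and ID status. This part stands, and it limits the point. A reader might infer that Appendix II is equally wrong after a restricted therapy (protocol 7.7.2), a code break (protocol 6.3) or pregnancy, where the protocol says "Discontinuation of study treatment is also mandatory in the case a subject enrolled into the study is getting pregnant". The documents do not support calling those cases errors: neither dosing table carries such a stop, and none of them is a weight, Hb or ID rule. Whether to zero later planned doses there is an optional choice of compliance definition. The Hb stop differs because it is an Hb rule written into the table that defines the planned dose.

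It is also fair to say that the subset is narrow, and that disposition tables and subject listings let a careful reader find these cases. That reduces the importance. It does not correct the summary tables.

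**Conclusion.** The conflict is real and should be corrected, but its effect is minor. It is confined to the Netherlands, Spain and Singapore under protocols 2 and 3. Table 6, for protocol 1, has no such footnote, so the SAP does not contradict itself there. It matters only when Hb falls below 10 g/dL at Week 6 or 12 and a later dosing visit shows recovery with ID. Affected subjects score 33% to 75% where 100% is right.

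Three stronger readings are not supported:
- **Frequency.** Twelve of 18 patterns is not a proportion of patients. The documents do not give the number of affected subjects.
- **Analysis sets and efficacy.** Appendix I excludes subjects with missed doses from the per-protocol set (PDIMP03), so a reader might infer that Appendix II feeds that exclusion. SAP 3.2 takes exclusions from the sponsor's deviation file and does not say that it is built from Appendix II. Compliance is tabulated on the Safety Set only, and no efficacy analysis uses it.
- **Bias between arms.** A difference is possible, but the documents give no rates from which to size it.

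The conclusion rests on reading the expected amount as the sum of the Appendix II planned doses, with Table 7 in force under protocols 2 and 3.

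**What to change.** In the row of Appendix II for the three countries, add for protocols 2 and 3: once Hb below 10 g/dL is recorded after enrolment, the planned dose is no dose at that visit and at all later visits. Use this planned dose consistently in the exposure summary, the by-visit dosing table and the compliance rate, so that the outputs do not carry two different planned volumes. In the same edit, let the definition of the expected amount name Table 7 as well as Table 6.

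The cost is one line of specification and the matching code. The rule uses Hb values already collected, so it needs no discontinuation reason codes and no case review. Patient care, efficacy analyses and analysis sets do not change. The downside is that the compliance rate will no longer show the volume lost to this stop. The stop itself stays visible in the disposition table, which reports treatment discontinuations with their reasons (SAP 4.4).

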4.8.6. Vital Signs

Vital signs include height (cm) (only at baseline), weight (kg), systolic blood pressure (mmHg), diastolic blood pressure (mmHg), heart rate (beats/min), pulse (beats/min), and temperature ($^{\circ}$ C) (only at baseline). They are assessed at Day 0, Week 6, Week 12, Week 24, and Week 52. Please see Appendix III for a description of parameter, unit and number of decimals to be displayed in summary tables.

Actual values and changes from baseline will be summarized at each visit, as done for laboratory data, for each vital sign parameter. Baseline is defined in section 4.2.12. Actual values of weight will also be summarised by category (<70 kg, \geq 70 kg) at each visit.

By-subject listings of vital signs measurements will be presented.

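### SAP Appendix II does not label the Visit 3 weight for protocols 2 and 3, so its closest-value note selects the Week 6 weight instead of baseline; separately, SAP 4.8.1 takes the compliance denominator from the protocol 1 table

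*SAP*

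**What the plan says.** **Dosing rule.** SAP 4.8.1 assigns subjects to a dosing table by protocol version: "Table 7 will apply only for subjects who consented to protocol 2 or 3", or who re-consented to protocol 2, for injections from that date on. For them the Week 6 dose "is based on the iron need upon screening Hb and weight values to replete iron as described in Table 7". Table 7, footnote 2, agrees: "Dosing at Week 6 (Visit 3) will be based on the iron need upon screening Hb and weight values and only be done in subjects" whose Week 6 Hb is no higher than 15 g/dL. Protocol Table 1, footnote 2, has the same rule, and Protocol 9.2.2.1 ties the Week 6 dose to the iron need found at baseline. Weight is first recorded at the baseline visit (Protocol 9.2.1.2 and Table 2), not at Visit 1, so the weight meant is the baseline weight.

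**Algorithm.** SAP 4.8.1 sends the planned-dose calculation to Appendix II. The Visit 3 block for protocols 2 and 3 has four dose-band lines, for example "Weight in kg' ≥ 70 and 10 ≤ 'Hemoglobin (from screening) in g/dL' ≤ 14 : 1 Kit". In all four, Hb is labelled as the screening value and weight is not. The block ends with "Hemoglobin in g/dL' > 14 : No dose", also unlabelled. Two general lines above the visit blocks give no dose for Hb below 8 or above 15 g/dL. The note beneath the table says: "The laboratory and vital sign values closest to the injection date and time (\leq) is used". SAP 4.8.1 carries the same rule ("The laboratory and vital sign values closest to the injection date and time"), and uses the value nearest the visit if no injection was given. SAP 4.8.6 counts weight among the vital signs: "They are assessed at Day 0, Week 6, Week 12, Week 24, and Week 52".

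**Compliance.** SAP 4.8.1 classes each dose as given as planned, reduced or increased. It computes compliance as total over expected amount × 100, grouped as <80, 80–120 and >120. The expected amount refers to Table 6 alone. Table 6 is the protocol 1 regimen and gives a Week 6 dose only if iron deficiency (ID) persists. Table 7 has no such condition at Week 6.

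**The concern.** The dosing rule fixes the Week 6 dose on baseline values. The written algorithm overrides the closest-value note for Hb but not for weight. A programmer who follows it would compare a dose chosen on baseline weight with a plan computed from Week 6 weight. A correctly dosed subject whose weight has crossed 70 kg would then be reported as over- or under-dosed.

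The unlabelled Hb lines in the same block create smaller conflicts with Table 7. The Table 6 reference applies a protocol 1 condition to subjects who were never subject to it.

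At stake are the exposure and compliance tables 14.1.10.1 and 14.1.10.2 and listing 16.2.5.2, all on the Safety Set.

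**Working it through.** **Inputs.** From Table 7: Visit 2 dose 20 mL for Hb 8–14 g/dL and 10 mL for Hb above 14; Visit 3 dose by weight and Hb band; 10 mL at each of Weeks 12 and 24 if ID persists. Table 6 has the same volumes, but a Week 6 dose only if ID persists. The weights of 68 and 72 kg, the Hb values and the ID status below are illustrative assumptions.

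**Step 1: reproduce Table 7.** Appendix II with baseline weight and screening Hb, Week 6 Hb no higher than 14, gives these Visit 3 doses (mL):

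| Baseline weight | Hb 9 | Hb 12 | Hb 14.5 |
|---|---|---|---|
| 68 kg | 10 | 0 | 0 |
| 72 kg | 20 | 10 | 0 |

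All six match Table 7. In the last column no Appendix II line strictly matches; I read that as no dose.

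**Step 2: use the Week 6 weight, as the note directs.** Doses are given correctly per Table 7; Week 6 Hb equals screening Hb.

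| Weight, baseline → Week 6 | Hb | Given | Planned | Class |
|---|---|---|---|---|
| 72 → 68 kg | 9 | 20 mL | 10 mL | increased |
| 72 → 68 kg | 12 | 10 mL | 0 mL | increased |
| 68 → 72 kg | 9 | 10 mL | 20 mL | reduced |
| 68 → 72 kg | 12 | 0 mL | 10 mL | reduced (natural reading; not stated) |

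If these planned doses also formed the expected amount, compliance with m maintenance doses would be (20 + given + 10m) / (20 + planned + 10m):

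| Case | m = 0 | m = 1 | m = 2 |
|---|---|---|---|
| 72 → 68 kg, Hb 9 | 40/30 = 133% | 50/40 = 125% | 60/50 = 120% |
| 72 → 68 kg, Hb 12 | 30/20 = 150% | 40/30 = 133% | 50/40 = 125% |
| 68 → 72 kg, Hb 9 | 30/40 = 75% | 40/50 = 80% | 50/60 = 83% |
| 68 → 72 kg, Hb 12 | 20/30 = 67% | 30/40 = 75% | 40/50 = 80% |

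With no maintenance dose all four leave the 80–120 band; with two, only one does. The Visit 3 class is wrong throughout.

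**Step 3: the unlabelled Hb lines.**
- At 70 kg or more, screening Hb 12 and Week 6 Hb 14.5 match both the one-kit line and the final no-dose line. Table 7, footnote 2, allows dosing up to 15 g/dL.
- Screening Hb 14.5 with Week 6 Hb 13.5 matches no line. Labelling the last line as screening Hb would give no dose, as in Table 7.
- Week 6 Hb below 8 g/dL gives no dose under the general line. Table 7 states no lower Week 6 limit outside the Netherlands, Spain and Singapore; in the SAP 4.8.1 text the lower limit attaches to Weeks 12 and 24.

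**Step 4: Table 6 as denominator.** Subject under protocol 2 or 3, dosed per Table 7, ID absent at Week 6, weight and Hb bands unchanged. With Visit 2 dose D and Table 7 Week 6 dose d, compliance = (D + d + 10m) / (D + 0 + 10m).

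| Band | D, d | m = 0 | m = 1 | m = 2 |
|---|---|---|---|---|
| ≥70 kg, Hb 8–<10 | 20, 20 | 40/20 = 200% | 50/30 = 167% | 60/40 = 150% |
| ≥70 kg, Hb 10–14 | 20, 10 | 30/20 = 150% | 40/30 = 133% | 50/40 = 125% |
| <70 kg, Hb 8–<10 | 20, 10 | 30/20 = 150% | 40/30 = 133% | 50/40 = 125% |
| <70 kg, Hb 10–14 | 20, 0 | 100% | 100% | 100% |
| Screening Hb >14 | 10, 0 | 100% | 100% | 100% |

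Against Table 7 every row is 100%.

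**The case against.** **Table 7 is the specific rule and should override a general note.** This is a reasonable reading, and a careful programmer might adopt it. But Appendix II is the stated algorithm, the closest-value rule is repeated in the main text, and the exception is written for Hb only. The deviation list in SAP Appendix I blurs the matter: its code for incorrect post-baseline dosing speaks of body weight and Hb at those visits. That code also covers protocol 1, and Protocol 9.2.2.1 is clear about baseline. If no Week 6 weight exists at or before the injection, the note falls back to an earlier one and the fault may not arise.

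**Table 6 is a slip.** Probably so. Elsewhere SAP 4.8.1 cites Tables 6 and 7 together for the planned amounts. It is still the only definition given for the denominator.

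**A reader might infer that every crossing of 70 kg produces a 10 mL error.** It does not. Nothing changes if screening Hb is above 14, Week 6 Hb is above 15 or the pregnancy test is positive. For Week 6 Hb above 14 and up to 15, if the final line prevails, the gap is 20 mL for 72 → 68 kg with Hb 9 and zero for 68 → 72 kg with Hb 12.

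**A reader might infer that the per-protocol set is contaminated.** Incorrect dosing does exclude subjects from it. But SAP 3.2 has the deviation file produced separately, and nothing says that it is derived from Appendix II.

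**The lower limit of 8 g/dL has little reach.** Accepted: a subject who needs transfusion must stop study treatment anyway (Protocol 7.7.2).

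**Conclusion.** Wrong as written, and minor. The weight fault shifts the planned Week 6 dose by 10 mL for subjects under protocols 2 and 3 with screening Hb 8–14 g/dL whose weight crosses 70 kg, provided Week 6 Hb is 8–14 g/dL (10–14 in the Netherlands, Spain and Singapore) and no pregnancy test is positive. The Table 6 reference, taken literally, puts subjects dosed per Table 7 with ID absent at Week 6 into the >120 category at 125–200%, apart from the two 100% bands in Step 4.

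The effect is limited to the descriptive Safety Set exposure and compliance outputs. No effect on the full analysis set, the per-protocol set or any efficacy estimate is shown. The derivation code is not in the documents, so this is a fault in the written rule, not evidence that any subject was misreported or misdosed.

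A reader might infer a false excess of over-dosing on ferric carboxymaltose. The direction is plausible, since Protocol 1.2 reports consistent repletion of iron stores, which would make ID absent at Week 6 commoner in that arm. The size of any difference, like the number of subjects affected, cannot be derived from the documents.

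**What to change.** Before unblinding, in SAP Appendix II, Visit 3, protocols 2 and 3:
- use baseline weight in the four dose-band lines and exempt it from the closest-value note, there and in 4.8.1;
- label the last line as screening Hb above 14;
- keep the Week 6 Hb above 15 g/dL and pregnancy-test gates;
- apply no lower Week 6 Hb limit, except the withdrawal rule below 10 g/dL in the Netherlands, Spain and Singapore.

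In SAP 4.8.1, define the expected amount by Table 6 or Table 7 according to the protocol version applicable at the injection. Update the derivation code to match.

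The cost is a few words in the appendix, one line in 4.8.1 and the matching code. Patients and sites are not affected.
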